APPENDIX VIII: TEMOZOLOMIDE CAPSULE DOSING (100 MG/M²) NOMOGRAM

Use this nomogram for patients whose BSA is at least 0.6 m² receiving capsule formulation. For patients with BSA <0.6 m², please see dosing table in the treatment section of the protocol.

Example: For a patient with BSA of 0.66 m², the calculated dose is 0.66 m² x 100 mg/m² = 66 mg/day; administered dose per nomogram = 65 mg temozolomide/day.

BSA (m ²)	Calculated daily dose (mg)	Administered daily dose (mg)
0.6-0.62	58-62	60
0.63-0.67	63-67	65
0.68-0.72	68-72	70
0.73-0.77	73-77	75
0.78-0.82	78-82	80
0.83-0.87	83-87	85
0.88-0.92	88-92	90
0.93-0.97	93-97	95
0.98-1.0	98-100	100
1.01-1.05	100-105	105
1.06-1.14	106-114	110
1.15-1.24	115-124	120
1.25-1.34	125-134	130
1.35-1.44	135-144	140
1.45-1.54	145-154	150
1.55-1.64	155-164	160
1.65-1.74	165-174	170
1.75-1.84	175-184	180
1.85-1.94	185-194	190
1.95-2.00	195-200	200
> 2.0	> 200	200

APPENDIX IX: TEMOZOLOMIDE REDUCED (75 MG/M²) DOSING NOMOGRAMS

For patients with BSA < 0.6 m² who require a dose reduction, use the table below.

The dose of temozolomide in the table is expressed as final dose in **mg** to be administered.

TEMOZOLOMIDE Dose Reduction If BSA < 0.6 m²	
BSA (m ²)	Dose
0.25-0.29	10 mg
0.30-0.34	15 mg
0.35-0.39	20 mg
0.40-0.44	25 mg
0.45-0.49	30 mg
0.50-0.54	35 mg
0.55-0.59	40 mg

Use the nomogram below for patients whose BSA is at least 0.6 m² receiving capsule formulation.

Example: For a patient with a BSA of 0.66 m², the calculated dose = 49.5 mg/dose; administered dose per nomogram = 50 mg temozolomide/dose.

BSA (m ²)	Calculated daily dose (mg)	Administered daily dose (mg)
0.6-0.63	43-47	45
0.64-0.70	48-52	50
0.71-0.76	53-57	55
0.77-0.83	58-62	60
0.84-0.90	63-67	65
0.91-0.96	68-72	70
0.97-1.03	73-77	75
1.04-1.10	78-82	80
1.11-1.16	83-87	85
1.17-1.23	88-92	90
1.24-1.30	93-97	95
1.31-1.36	98-102	100
1.37-1.43	103-107	105
1.44-1.50	108-112	110
1.51-1.56	113-117	115
1.57-1.63	118-122	120
1.64-1.70	123-127	125
1.71-1.76	128-132	130
1.77-1.83	133-137	135
1.84-1.90	138-142	140
1.91-1.96	143-147	145
≥ 1.97	148	150

APPENDIX X: SUMMARY OF BIOLOGIC CORRELATIVE LAB STUDIES

Time point	Sample Type ^b	Volume per tube ^c	Quantity	Tube Type / Sample Prep	Notes	Destination Lab	Section Number	
CORRELATIVE STUDIES: POST-CONSOLIDATION	Pre-therapy	Blood	5 mL	2 tubes	Sodium heparin (Green top) tube	REQUIRED; Ship same day Immune Phenotyping	Emory	14.1.1
			5 mL	1 tube	Sodium heparin (Green top) tube	REQUIRED; Process for plasma Cytokine Analysis	Emory	14.1.2
			2 mL	1 tube	EDTA	Process for plasma Batch ship	BPC	14.2.1.1
			10 mL	1 tube	Streck Cell Free DNA tube ^a	Ship same day	BPC	14.2.1.2
			2.5 mL	1 tube	PAXgene RNA tube ^a	Ship same day	BPC	14.2.1.3
	Cycle 1, post completion of dinutuximab (collect single sample between Day 5-Day 8)	Blood	5 mL	2 tubes	Sodium heparin (Green top) tube	REQUIRED; Ship same day Immune Phenotyping	Emory	14.1.1
			5 mL	1 tube	Sodium heparin (Green top) tube	REQUIRED; Process for plasma Cytokine Analysis	Emory	14.1.2
	Cycle 2, Day 1	Blood	5 mL	2 tubes	Sodium heparin (Green top) tube	REQUIRED; Ship same day Immune Phenotyping	Emory	14.1.1
			5 mL	1 tube	Sodium heparin (Green top) tube	REQUIRED; Process for plasma Cytokine Analysis	Emory	14.1.2
			10 mL	1 tube	Streck Cell Free DNA tube ^a	Ship same day	BPC	14.2.1.2
			2.5 mL	1 tube	PAXgene RNA tube ^a	Ship same day	BPC	14.2.1.3
	Cycle 3, Day 1	Blood	2 mL	1 tube	EDTA	Process for plasma Batch ship	BPC	14.2.1.1
			10 mL	1 tube	Streck Cell Free DNA tube ^a	Ship same day	BPC	14.2.1.2
			2.5 mL	1 tube	PAXgene RNA tube ^a	Ship same day	BPC	14.2.1.3
	Cycle 6, Day 8	Blood	2 mL	1 tube	EDTA	Process for plasma Batch Ship	BPC	14.2.1.1
	End of therapy	Blood	5 mL	2 tubes	Sodium heparin (Green top) tube	REQUIRED; Ship same day Immune Phenotyping	Emory	14.1.1
		Blood	5 mL	1 tube	Sodium heparin (Green top) tube	REQUIRED; Process for plasma Cytokine Analysis	Emory	14.1.2
		Blood	10 mL	1 tube	Streck Cell Free DNA tube ^a	Ship same day	BPC	14.2.1.2
		Blood	2.5 mL	1 tube	PAXgene RNA tube ^a	Ship same day	BPC	14.2.1.3
	Relapse / Progression	Blood	5 mL	2 tubes	Sodium heparin (Green top) tube	REQUIRED; Ship same day Immune Phenotyping	Emory	14.1.1
Blood		5 mL	1 tube	Sodium heparin (Green top) tube	REQUIRED; Process for plasma Cytokine Analysis	Emory	14.1.2	

	Blood	10 mL	1 tube	Streck Cell Free DNA tube ^a	Ship same day	BPC	14.2.1.2
	Blood	2.5 mL	1 tube	PAXgene RNA tube ^a	Ship same day	BPC	14.2.1.3

- a. If the patient has consented to optional banking studies, both PAXgene RNA tubes and Streck Cell Free DNA BCT tubes should be ordered via the BPC Kit Management system as soon as possible after patient enrollment to allow time for tubes to be shipped. Please see [Section 14.2.1.2](#) for contact information.
- b. Please refer to appropriate section regarding blood volume adjustments if applicable.
- c. Prioritization of samples if blood volumes approach maximum allowance per institutional standards for small children.
 1. Required samples (sodium heparin [Green top] tubes)
 2. EDTA tube
 3. Streck Cell Free DNA tube
 4. PAXgene RNA tube

Please refer to appropriate section regarding blood volume adjustments if applicable.

APPENDIX XI: EMERGENCY MANAGEMENT OF DINUTUXIMAB TOXICITIES

This document is for rapid reference. See [Section 5.2.5](#) for further information regarding management of acute toxicities during dinutuximab-containing cycles of therapy.

Severe Allergic Reaction

Definition (any of the following): symptomatic bronchospasm with or without urticaria, IV meds required, allergy-related edema/angioedema, or anaphylaxis (Grade 3 or 4).

Treatment:

- Immediately **hold** dinutuximab infusion
- Assess airway, breathing and circulation

For airway concerns:

- Administer oxygen and albuterol immediately for bronchospasm
- Administer diphenhydramine (if not already being given)
- Administer epinephrine immediately if upper airway involved or if airway issues are accompanied by cardiovascular collapse
- Administer hydrocortisone **if any of the following are true**
 - patient has frank anaphylaxis with cardiorespiratory collapse
 - two or more doses of epinephrine are required
 - moderate to severe symptoms recur upon rechallenge with dinutuximab

For hypotension in setting of allergic reaction:

- Hold dinutuximab and give normal saline bolus (see hypotension guidelines)
- Stop or adjust doses of narcotics
- For patients with hypotension that resolves with initial volume bolus, resume dinutuximab at half rate

Reassess need for additional volume resuscitation, ICU transfer and use of vasopressors.

For patients with angioedema that does **not** affect the airway or patients with mild bronchospasm and **no** other symptoms:

- If symptoms resolve rapidly, dinutuximab can be resumed at half rate with very close observation

Minimal criteria for resumption of dinutuximab infusion:

- Complete resolution of airway symptoms
- Complete resolution of hypotension

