 - If hypotension recurs at the reduced rate, the measures above should again be taken and no further dinutuximab should be given that day. The antibody infusion may be restarted the following day after ensuring that the patient is volume replete. The antibody rate upon resumption of treatment should be 50% of the initial rate. If blood pressures are stable for 2 hours, the infusion may be given at full rate for that day and subsequent days. If the patient's blood pressures are only stable at the 50% rate and not at full rate, the

remaining days' doses of dinutuximab should be given at the 50% rate of infusion.

- iii. For patients who require pressors for treatment of hypotension, if blood pressure is stable off pressors for at least 6 hours, administration of dinutuximab may be resumed at 50% of the initial infusion rate on the day following the hypotensive episode. Care should be taken to ensure that the patient is volume replete. Dinutuximab should not be given to patients who continue to require pressor support. Patients who require pressor support for ≥ 24 hours due to treatment-related hypotension despite appropriate volume resuscitation should discontinue protocol therapy. Patients who again require pressor support when dinutuximab is resumed must discontinue protocol therapy.

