5.2.5.2 Treatment of allergic reactions/infusion reactions

- a. Mild allergic reactions/infusion reactions to dinutuximab infusion
 - i. A mild allergic reaction is limited to rash, flushing, urticaria, mild dyspnea – Grade 1 or 2
 - ii. The following recommendations do NOT apply to Grade 3 or 4 allergic reactions, including anaphylaxis
 - iii. Management
 - Decrease rate of dinutuximab to 50% of full rate
 - Perform serial exams at bedside
 - Administer H1 blocker (diphenhydramine, cetirizine recommended)
 - Administer H2 blocker
 - When symptoms resolve, resume original infusion rate
 - If symptoms recur when original rate is resumed, decrease to 50% rate again
 - Infusion must be stopped after 20 hours (whether the full dose of dinutuximab has been administered or not); document total amount of drug given in the 20 hour time period.
- b. Moderate to severe allergic reactions/infusion reactions to dinutuximab infusion
 - i. Moderate to severe reactions include any of the following: symptomatic bronchospasm, allergy-related edema/angioedema, hypotension, or anaphylaxis – Grade 3 or 4
 - ii. The following recommendations do NOT apply to Grade 1 or 2 allergic reactions
 - iii. Management
 - **Immediately hold dinutuximab**
 - Assess airway, breathing and circulation
 - Follow institutional guidelines for rapid response team notification if clinically indicated
 - For airway concerns

- Administer oxygen and albuterol immediately for bronchospasm
- Administer IV diphenhydramine
- Administer epinephrine (1:1000 IM recommended) immediately if upper airway involved or if airway issues are accompanied by cardiovascular collapse
- Administer IV hydrocortisone (1-2 mg/kg) if the patient has frank anaphylaxis with cardiorespiratory collapse OR if ≥ 2 doses of epinephrine are required OR if moderate to severe symptoms recur upon rechallenge with dinutuximab
- For hypotension in the setting of allergic reaction
 - Give normal saline bolus (20 mL/kg as rapidly as possible)
 - Stop or adjust doses of narcotics and sedating H1 blockers
 - Consider use of Trendelenberg position
 - See previous section for management of persistent hypotension

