- For patients with mild bronchospasm or angioedema that does not impact breathing, completely resolves without the use of epinephrine and hydrocortisone and for patients whose hypotension resolves following volume bolus, dinutuximab may be resumed at 50% of the previous rate of infusion on the same day as the reaction occurred. If symptomatic angioedema or asymptomatic bronchospasm recurs when the dinutuximab is restarted, discontinue immunotherapy for that day and if symptoms/signs resolve completely that day, resume the next day with additional pre-medication of hydrocortisone 1-2 mg/kg IV. For this re-challenge, the infusion should be given in an ICU setting.
- For patients whose bronchospasm or angioedema requires the use of systemic epinephrine, protocol therapy must be discontinued.
- For patients with bronchospasm or angioedema that does not require systemic epinephrine but whose hypotension requires more extensive volume resuscitation, guidance in [Section 5.2.5.1](#) should be followed.

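### The Appendix XI bedside sheet leaves out the Section 5.2.5.2 stop after systemic epinephrine, so a child who must come off protocol therapy could be restarted at half rate

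*Combined protocol and SAP*

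**What the plan says.** Section 5.2.5.2(b) sets the rules for moderate to severe allergic reactions to dinutuximab. It allows same-day restart at 50% of the previous rate for two groups. The first has mild bronchospasm or angioedema that does not affect breathing and that "completely resolves without the use of epinephrine and hydrocortisone". The second has hypotension that resolved after a volume bolus. The stop rule is a separate bullet immediately after this permission: "For patients whose bronchospasm or angioedema requires the use of systemic epinephrine, protocol therapy must be discontinued".

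Appendix XI condenses this for use in an emergency. On epinephrine it says: "Administer epinephrine immediately if upper airway involved or if airway issues are accompanied by cardiovascular collapse". For hypotension within an allergic reaction it says: "For patients with hypotension that resolves with initial volume bolus, resume dinutuximab at half rate". A separate line allows half-rate restart, with close observation, for angioedema that spares the airway or for mild bronchospasm with nothing else, if symptoms resolve quickly. The sheet closes with a list headed "Minimal criteria for resumption of dinutuximab infusion", which has two entries: airway symptoms completely resolved, and hypotension completely resolved. It says nothing about stopping after epinephrine.

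Sections 4.4.7 and 4.5.7 tell staff to obtain this material before starting dinutuximab and recommend having it on the unit to support treatment decisions. The header of Appendix XI calls it a rapid reference and sends the reader to Section 5.2.5 for more information.

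**The concern.** The sheet carries over the permission to restart but not the prohibition that follows it in the body text. It also states the restart as an instruction, where Section 5.2.5.2 says only that the infusion may be resumed. A clinician managing an acute reaction from the sheet alone could re-expose a child to the antibody on the day of a reaction serious enough to need epinephrine, when the protocol requires protocol therapy to end. The protocol treats re-exposure after such reactions seriously elsewhere: exclusion 3.2.22 bars patients whose earlier reaction to an anti-GD2 antibody was Grade 4 or led to its discontinuation. What is at stake is patient safety.

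**Working it through.** No arithmetic applies. The check follows one case through both texts.

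The case: during the infusion a child develops angioedema involving the upper airway, together with hypotension. Systemic epinephrine is given. The airway clears completely and blood pressure recovers fully after the first saline bolus.

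| Step | Appendix XI | Section 5.2.5.2(b) |
|---|---|---|
| Upper airway involved | Hold infusion, give epinephrine | Hold infusion, give epinephrine (intramuscular route recommended) |
| Systemic epinephrine was needed for angioedema | No consequence for restart stated | Protocol therapy must end |
| Hypotension cleared with the first bolus | Resume at half rate | 50% restart the same day is permitted in general, but the mandatory stop applies to this child |
| Airway and pressure fully recovered | Both minimal criteria met | Does not lift the stop |
| Result | Half-rate restart | Off protocol therapy |

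Three further checks fix where the conflict lies.

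1. *The hypotension line on its own.* Section 5.2.5.2 also allows a 50% restart when hypotension resolves after a bolus, and the sheet's reference to the initial bolus is, if anything, slightly narrower. The sentence is not wrong in itself. The fault is the missing exclusion.

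2. *The airway restart line.* It covers only angioedema that spares the airway, or mild bronchospasm with no other symptoms. The child above is outside it. Under the sheet's own indications, a child inside it would not normally have received epinephrine on a first reaction. The conflict therefore runs through the hypotension line and the minimal criteria, not through this line.

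3. *The pressor rules.* For persistent hypotension Section 5.2.5.2 says: "See previous section for management of persistent hypotension". That leads to Section 5.2.5.1, where restart after pressors waits until the following day and is allowed only "if blood pressure is stable off pressors for at least 6 hours", with discontinuation if pressors are needed for 24 hours or more or are needed again on restart. The sheet mentions pressors only as a need to reassess. A child who required pressors did not have hypotension that resolved with the initial bolus, so the sheet's restart line does not apply. This is silence, not contradiction.

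**The case against.** The strongest reply is that Appendix XI is a summary and is not meant to repeat every rule. Its header points to Section 5.2.5, Section 8.1 defines removal for toxicity by reference to Section 5.0, and each therapy delivery map sends staff to Section 5.0 for dose modifications. The conflict also needs a particular combination: an upper-airway reaction, epinephrine, and hypotension that clears with one bolus. It requires applying the hypotension line although the airway restart line would not admit the child. Finally, minimal criteria can be read as necessary conditions rather than as permission.

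Much of this stands. Section 5.2.5.2 is clear, is one reference away, and remains the operative standard. A reader might infer that the appendix sets up a rival stopping rule; the documents do not support that.

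It does not remove the point. The header offers Section 5.2.5 as further information and does not warn that a mandatory stop is absent. The hypotension line is worded as an instruction, and the sheet names no criterion beyond the two listed. The sheet is intended for the moment when staff are least likely to look up the body text.

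Two other inferences go too far. One is that the missing pressor rules could produce a wrong restart through the quoted line; they cannot, for the reason given in the third check. The other is that dropping the condition on epinephrine and hydrocortisone from the airway restart line opens that line to treated children; its narrow scope already implies most of that condition.

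**Conclusion.** The point holds: Appendix XI omits one mandatory stop rule, and at least one clinically coherent case meets its restart line and both its criteria while Section 5.2.5.2 requires discontinuation. This should be corrected on safety grounds.

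The conclusion assumes that the epinephrine given under the sheet is systemic, as the body text recommends, and that staff act on the sheet without opening Section 5.2.5.

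A reader might infer that wrong restarts would be frequent, or would distort the feasibility rate, because Section 9.3.1 counts patients who meet off-protocol criteria before completing 5 cycles against feasibility. The documents do not support either inference. Section 4.4.3 describes allergic reactions as common with this antibody, but without regard to grade, and no figure is given for reactions that need epinephrine.

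**What to change.** Under the resumption criteria in Appendix XI add a line such as: *Do not restart dinutuximab if systemic epinephrine was needed for bronchospasm or angioedema; take the patient off protocol therapy (Section 5.2.5.2).* In the header, state that Section 5.2.5 governs wherever the two texts differ.

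Two further edits are optional tidying: add to the airway restart line the condition that symptoms resolved without epinephrine and hydrocortisone, and add a pointer to Section 5.2.5.1 for hypotension and the pressor rules.

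The cost is a wording change in one appendix and reissue of the bedside sheet. No patients, visits or assays are affected.

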APPENDIX XII: CURIE SCORING SUMMARY SHEET

COG Registration Number: _____ **Radiology reviewer:** _____
(6 digits) *(print name)*

Date of scan: _____ **Type of Scan** (check 1): I-123 MIBG I-131 MIBG
(DD/MM/YYYY)

Scan time point (circle 1): Baseline End of Cycle 3 End of therapy

Off therapy Surveillance (months from end of therapy):
 3 6 12 18 24 36

Relapse/Progression

Other (specify):

[figure not shown]
Table 1a. Scoring skeletal disease

Regions 1 – 9	
Scoring	MIBG uptake
0	No MIBG uptake
1	1 focal site
2	> 1 focal site
3	≥ 50% of a region

Table 1b. Scoring soft tissue disease

Region 10 (Primary soft tissue site)	
Scoring	MIBG uptake
0	No soft tissue uptake
1	1 focal soft tissue site
2	> 1 focal soft tissue site
3	≥ 50% of a region (chest, abdomen)

Region	Site	Curie score
1	Head / Neck	
2	Cervico-Thoracic spine	
3	Ribs / Sternum / Clavicles/ Chest	
4	Lumbar / Sacral spine	
5	Abdomen/Pelvis	
6	Upper Extremity (Proximal)	
7	Upper Extremity (Distal)	
8	Lower Extremity (Proximal)	
9	Lower Extremity (Distal)	
10	Soft Tissue	
TOTAL	Total scores from Regions 1 - 10	

APPENDIX XIII: OVERALL RESPONSE CRITERIA

Primary Tumor	Soft Tissue and Bone Metastatic Disease (MIBG or FDG-PET/CT or PET/MR)	Bone Marrow Metastatic Disease	Overall
CR	CR	CR	CR
CR for one response component with either CR or NI for other components			CR
CR	CR	MD	PR
CR	PR	CR	PR
CR	PR	MD	PR
CR	PR	NI	PR
CR	NI	MD	PR
PR	CR	CR	PR
PR	CR	NI	PR
PR	CR	MD	PR
PR	PR	CR	PR
PR	PR	NI	PR
PR	PR	MD	PR
PR	NI	CR	PR
PR	NI	NI	PR
PR	NI	MD	PR
NI	CR	MD	PR
NI	PR	CR	PR
NI	PR	MD	PR
CR	CR	SD	MR
CR	PR	SD	MR
CR	SD	CR	MR
CR	SD	MD	MR
CR	SD	SD	MR
CR	SD	NI	MR
CR	NI	SD	MR
PR	CR	SD	MR
PR	PR	SD	MR
PR	SD	CR	MR
PR	SD	MD	MR
PR	SD	SD	MR
PR	SD	NI	MR
PR	NI	SD	MR
SD	CR	CR	MR
SD	CR	MD	MR
SD	CR	SD	MR
SD	CR	NI	MR
SD	PR	CR	MR
SD	PR	MD	MR
SD	PR	SD	MR
SD	PR	NI	MR
SD	SD	CR	MR
SD	NI	CR	MR
NI	CR	SD	MR
NI	PR	SD	MR
NI	SD	CR	MR
SD	SD	MD	SD
NI	SD	MD	SD
SD	NI	MD	SD
NI	NI	MD	SD
SD	SD	SD	SD
SD	NI	SD	SD
NI	SD	SD	SD
NI	SD	NI	SD
NI	NI	SD	SD
PD in any one component			PD
Response of Not Evaluable for any one of the 3 components that had measurable/evaluable tumor at study enrollment and no PD for any component			Not Evaluable
No response evaluation performed for any of the 3 components			Not Done

CR: Complete Response; MD: Minimal Disease; PR: Partial Response; MR: Minor Response; SD: Stable Disease; PD: Progressive disease; NI: not involved; site not involved at study entry and remains not involved.

